2.3. Radionuclide-chelating PSMA ligands

Targeted radionuclide therapy (both monoclonal antibody and/or urea based peptides) is a state of the art and rapidly developing therapy option for different cancer types. The potential advantage of targeted radionuclide therapy is saving the normal tissue while giving a high radiation dose to the tumor.

After rather unsuccessful therapy with ⁹⁰Y-CYT-356 monoclonal antibody (mAb) that binds to the intracellular domain of PSMA(Deb, Goris et al. 1996), phases 1 and 2 clinical trials utilizing the PSMA mAb J591, radiolabelled with ⁹⁰Y (Yttrium-90) or ¹⁷⁷Lu (Lutetium-177), have shown promising results(Bander, Milowsky et al. 2005, Vallabhajosula, Goldsmith et al. 2005, Vallabhajosula, Goldsmith et al. 2005, Tagawa, Milowsky et al. 2013).

Also, PSMA has recently been discovered as a promising target for radioisotope based approaches, both for PET imaging, for example, using 68Ga-labeled PSMA ligands(Afshar-Oromieh, Haberkorn et al. 2012, Afshar-Oromieh, Haberkorn et al. 2013, Afshar-Oromieh, Zechmann et al. 2014, Chakraborty, Tripathi et al. 2015, Eiber, Nekolla et al. 2015, Uprimny, Kroiss et al. 2015), and for therapy, for example, using ligands labeled with either β - or α -emitting nuclides such as ¹³¹I (Iodine-131), ¹⁷⁷Lu (Lutetium-177), and ²²⁵Ac (Actinium-225)(Zechmann, Afshar-Oromieh et al. 2014, Ahmadzadehfar, Rahbar et al. 2015, Kratochwil, Giesel et al. 2015). Despite encouraging early results, data about intended and unintended effects of PSMA- based radioligand therapies (RLTs) are still scarce.

2.3.1. Prior clinical experience with PSMA small molecule(s) in men with prostate cancer:

Results from selective clinical trials using radiolabeled PSMA ligand for diagnosis and treatment of prostate cancer are reported here under:

I. **^{68}Ga -PSMA:**

a) **Diagnostic value of ^{68}Ga -PSMA-HBED-CC PET/CT imaging in the diagnosis of recurrent prostate cancer(Afshar-Oromieh, Avtzi et al. 2015):**

The study reports data from a retrospective analysis of 319 patients who underwent ^{68}Ga -PSMA-ligand PET/CT from 2011 to 2014. The ^{68}Ga -PSMA-HBED-CC solution was applied to the respective patient via an intravenous bolus injection (mean of 172.4 MBq \pm 70.9, range 40 – 400 MBq, median 161 MBq). A non-contrast-enhanced CT scan was performed 1-hour post tracer injection. Histological verification was performed in 42 patients after the ^{68}Ga -PSMA-ligand PET/CT. Tracer uptake was measured in 901 representative tumor lesions. 82.8% of the patients had at least one lesion indicative of PC was detected. Tumor-detection was positively associated with PSA level and Androgen deprivation therapy (ADT). Gleason Score and PSA doubling time (PSA-DT) were not associated with tumor-detection. The average maximum standardized uptake value (SUVmax) of tumor lesions was 13.3 ± 14.6 (0.7-122.5). Amongst lesions investigated by histology, 30 were false-negative in 4 different patients, and all other lesions (n = 416) were true-positive or true-negative. A lesion-based analysis of sensitivity, specificity, negative predictive value (NPV) and positive predictive value (PPV) revealed values of 76.6%, 100%, 91.4% and 100%. A patient-based analysis revealed a sensitivity of 88.1%.

b) **PET imaging with a ^{68}Ga -PSMA ligand for the diagnosis of prostate cancer: biodistribution in humans and first evaluation of tumor lesions (Afshar-Oromieh, Malcher et al. 2013):**

Initial clinical studies with the ^{68}Ga -labeled PSMA-HBED-CC were conducted at Heidelberg University Hospital and the German Cancer Research Center to assess

the biodistribution of ^{68}Ga -PSMA-HBED-CC in normal tissues and tumor lesions. A total of 37 patients with prostate cancer and rising PSA levels were subjected to ^{68}Ga -PSMA-HBED-CC PET/CT imaging. Quantitative assessment of tracer uptake was performed 1 and 3 h post-injection by analysis of mean and maximum standardized uptake values (SUVmean/max) of several organs and 65 tumor lesions. Subsequently, tumor to background ratios were calculated.

The ^{68}Ga -PSMA-HBED-CC PET/CT images showed intense tracer uptake in both kidneys and salivary glands. Moderate uptake was seen in lacrimal glands, liver, spleen and in small and large bowel. Quantitative assessment revealed excellent contrast between tumor lesions and most normal tissues. Of 37 patients, 31 (83.8 %) showed at least one lesion suspicious for cancer at a detection rate of 60 % at PSA <2.2 ng/ml and 100 % at PSA >2.2 ng/ml. Median tumor to background ratios were 18.8 (2.4-158.3) in early images and 28.3 (2.9-224.0) in late images. Within healthy organs, kidneys and salivary glands demonstrated the highest radiotracer uptake. Lesions suspicious for prostate cancer presented with excellent contrast as early as 1-hour after injection with high detection rates even at low PSA levels.

c) **^{68}Ga -labeled PSMA ligand as superior PET tracer for the diagnosis of prostate cancer: Comparison with ^{18}F -FECH (Afshar-Oromieh, Haberkorn et al. 2012):**

This study was also published by the Heidelberg group, compared ^{68}Ga -PSMA-HBED-CC PET/CT imaging to standard choline-based PET/CT. Thirty-seven patients with biochemical relapse of prostate cancer [mean prostate-specific antigen (PSA) 11.1 ± 24.1 ng/ml, range 0.01-116] were retrospectively analyzed after ^{18}F -fluoromethylcholine and ^{68}Ga -PSMA PET/CT within a time window of 30 days. Radiotracer uptake that was visually considered as prostate cancer was semi-quantitatively analyzed by measuring the maximum standardized uptake values (SUVmax) of the scans acquired 1-hour after injection of ^{68}Ga -PSMA complex solution (median 132 MBq, range 59-263 MBq) and ^{18}F -fluoromethylcholine (median 237 MBq, range 114-374 MBq), respectively. In addition, tumor to background ratios were calculated.

The results showed a total of 78 lesions characteristic for prostate cancer that were detected in 32 patients using ^{68}Ga -PSMA-HBED-CC PET/CT imaging and 56 lesions were detected in 26 patients using choline PET/CT. The higher detection rate in ^{68}Ga -PSMA-HBED-CC PET/CT imaging was statistically significant ($p=0.04$). In five patients no lesion was found with both methods. All lesions detected by ^{18}F -fluoromethylcholine PET/CT were also seen by ^{68}Ga -PSMA-HBED-CC PET/CT imaging. In ^{68}Ga -PSMA-HBED-CC PET/CT imaging SUVmax was clearly (>10 %) higher in 62 of 78 lesions (79.1 %) and the tumor to background ratio was clearly (>10 %)

higher in 74 of 78 lesions (94.9 %) when compared to ¹⁸F-fluoromethylcholine PET/CT.

The authors concluded that ⁶⁸Ga-PSMA-HBED-CC PET/CT can detect lesions characteristic for prostate cancer with improved contrast when compared to standard ¹⁸F-fluoromethylcholine PET/CT, especially at low PSA levels.

d) Comparison of PET/CT and PET/MRI hybrid systems using a ⁶⁸Ga-labelled PSMA ligand for the diagnosis of recurrent prostate cancer: initial experience (Afshar-Oromieh, Haberkorn et al. 2014):

Subsequently, the Heidelberg group evaluated the feasibility of PET/MRI imaging with ⁶⁸Ga-PSMA-HBED-CC. Twenty patients underwent PET/CT 1-hour after injection of the ⁶⁸Ga-PSMA-HBED-CC followed by PET/MRI 3-hours after injection. Data from the two investigations were first analyzed separately and then compared with respect to tumor detection rate and radiotracer uptake in various tissues. To evaluate the quantification accuracy of the PET/MRI system, differences in SUVs between PET/CT and corresponding PET/MRI were compared with differences in SUVs between PET/CT 1-hour and 3-hours after injection in another patient cohort. This cohort was investigated using the same PET/CT system. With PET/MRI, different diagnostic sequences, higher contrast of lesions and higher resolution of MRI enabled a subjectively easier evaluation of the images. In addition, four unclear findings on PET/CT could be clarified as characteristic of prostate cancer metastases by PET/MRI. However, in PET images of the PET/MRI, a reduced signal was observed at the level of the kidneys (in 11 patients) and around the urinary bladder (in 15 patients). This led to reduced SUVs in six lesions. SUVmean values provided by the PET/MRI system were different in muscles, blood pool, liver and spleen.

The authors concluded that prostate cancer was detected more easily and more accurately with Ga-PSMA PET/MRI than with PET/CT and with lower radiation exposure. Consequently, this new technique could clarify unclear findings on PET/CT. However, scatter correction was challenging when the specific ⁶⁸Ga-PSMA- HBED-CC was used. Moreover, direct comparison of SUVs from PET/CT and PET/MR needs to be conducted carefully.

II. ¹⁷⁷Lu-PSMA-617:

a) ¹⁷⁷Lu-DKFZ-PSMA-617 therapy in metastatic castration resistant prostate cancer (Yadav, Ballal et al. 2016):

Thirty-one mCRPC patients with progressive disease despite second-line hormonal therapy and/or docetaxel chemotherapy were recruited for the study. All underwent ^{68}Ga -PSMA-HBED-CC PET/CT, prior to therapy with ^{177}Lu -DKFZ-PSMA-617. The mean activity administered was 5.07 ± 1.85 GBq ranging over one to four cycles. Study reported decline in PSA from baseline. Based on biochemical response criteria, 25/31 had either complete response, partial response or stable disease while 6 continued to have disease progression. The mean ECOG performance status improved from 2.54 to 1.78 after therapy. Two patients experienced grade I and grade II hemoglobin toxicity each, while none experienced nephrotoxicity or hepatotoxicity.

b) ^{177}Lu -PSMA-617 as A Novel Therapeutic Option in Patients With Metastatic Castration Resistant Prostate Cancer (Rahbar, Bode et al. 2016):

28 consecutive patients with mCRPC who have exhausted conventional therapeutic options were treated with 1 or 2 cycles of ^{177}Lu -PSMA-617. Mean administered activity at first therapy was 5.92 ± 0.44 GBq of ^{177}Lu -PSMA-617 and 5.86 ± 0.73 GBq at the second therapy. All patients underwent ^{68}Ga -PSMA-PET/CT prior to therapy. Any PSA decline occurred in 59% and 75% of patients after 1 and 2 Cycles. Similarly, a PSA decline of 50% or greater occurred in 32% and 50%. Hematologic and renal parameters changed insignificantly; permanent xerostomia or other safety-related toxicity did not occur. The estimated median survival was 29.4 weeks, which was significantly longer than survival in the historical best supportive care group.

c) PSMA-Targeted Radionuclide Therapy of Metastatic Castration-Resistant Prostate Cancer with ^{177}Lu -Labeled PSMA-617 (Kratochwil, Giesel et al. 2016):

^{177}Lu -PSMA I&T	56	3.6 – 8.7	1-5	Baum
^{177}Lu -PSMA-617	9	5.28 – 5.77	1	Hohberg
^{177}Lu -DKFZ-PSMA-617	5	3.4 – 3.9	2	Delker
^{177}Lu -DKFZ-PSMA-617	10	4.1- 6.1	1	Ahmadzedehfar
^{177}Lu -PSMA-617	7	5.5 - 7.4	1	Das
^{177}Lu -PSMA-617	23	7.4	1	Demir
^{177}Lu -PSMA-617	28	6	1-2	Rahbar
^{177}Lu -PSMA-617	31	1.1- 5.5	1-4	Yadav
^{177}Lu -PSMA I&T	1	8	1	Weineisen
^{177}Lu -PSMA I&T	22	3.4 – 7.4	1-4	Heck
^{177}Lu -PSMA-617	1	?	3	Schlenkhoff
^{177}Lu -PSMA-617	43	6	1-4	Zimbelmann
^{177}Lu -PSMA-617	5	5.8 – 7.4	1	Chakraborty

e) German collaborative publication

The largest published experience is a retrospective case series of 145 patients with mCRPC treated at 12 centers in Germany between February, 2014 and July, 2015.(Rahbar et al, J Nuc Med 2017) While not a prospective research study, in general the patients included men who had tumor progression despite abiraterone (64%) and/or enzalutamide (52%) and had either received chemotherapy (54%) or were unfit/refused chemotherapy. Patients also received radium-223 if able/eligible (17%). Treatment was administered only if PSMA uptake was demonstrated on PSMA imaging. On average, 5.9 GBq was administered per dose (range 2-8 GBq). Retreatment was allowed at physician discretion. Of assessable patients (n=99), 60% had PSA decline after initial treatment, with at least 50% PSA decline occurring in 40%. Safety was assessed by retrospective chart review with charts available in all 145 and labs available in 121 (83.4%). Grade >2 hematologic AEs occurred in 12% (grade 3/4 anemia in 10%, grade 3/4 leukopenia in 3%, and grade 3/4 thrombocytopenia in 4%). Other AEs of any grade that occurred $\geq 4\%$ include AST elevation 19%, fatigue 13%, renal failure 12%, ALT elevation 8%, xerostomia 8%, nausea 6%, dysgeusia 4%. While retrospective in nature, this represents the largest published series and demonstrates some biochemical anti-tumor activity without a high occurrence of high-grade adverse events.

2.4. Investigational Agent

During the last two decades, many efforts have been undertaken to develop PSMA-ligands(Hillier, Maresca et al. 2009, Barrett, Coleman et al. 2013). One of these ligands, the small molecule Glu-NH-CO-NH-Lys-(Ahx)-[⁶⁸Ga(HBED-CC)], also known as PSMA-11[®], PSMAHBED, Glu-CO-Lys(Ahx)-HBED-CC, DKFZ-PSMA-11, PSMA-HBED-CC,

PSMA-HBED, PSMA or ProstamedixTM, developed at the German Cancer Research

Center Heidelberg (DKFZ), has become the most clinically used radiotracer. This compound shows a strong binding affinity to PSMA as well as a highly efficient internalization into PCa cells(Eder, Schafer et al. 2012, Eder, Neels et al. 2014). PET/CT-imaging with ⁶⁸Ga-PSMA-11 has demonstrated this novel method as an important imaging modality for diagnosing recurrent PCa(Afshar-Oromieh, Haberkorn et al. 2014, Afshar-Oromieh, Zechmann et al. 2014, Afshar-Oromieh, Avtzi et al. 2015, Eiber, Maurer et al. 2015). Perera et al., did systematic review of ⁶⁸Ga-PET articles and Sixteen articles involving 1309 patients were analyzed. On per-patient analysis, the summary sensitivity and specificity were both 86%. On per lesion analysis, the summary sensitivity and specificity were 80% and 97%, respectively(Perera, Papa et al. 2016).

Meanwhile modifications of PSMA-11 have resulted in the development of another novel small molecule PSMA-ligand, PSMA-617. In preclinical studies, this ligand showed a significantly improved binding affinity to PSMA as well as a highly efficient internalization into PCa cells(Benesova, Schafer et al. 2015). PSMA-617 can be labeled with radionuclides like ⁶⁸Ga(Gallium-68), ¹⁷⁷Lu(Lutetium-177), ¹¹¹In(Indium-111), and ⁹⁰Y(Yttrium-90) and, therefore, be used for PET-imaging as well as for radioligand-based therapy. Preclinical assays of PSMA-617 showed Ki values of 2.3 ± 2.9 nM, demonstrating a significant improvement compared to PSMA-11 (12.0 ± 2.8 nM). Based on these results, PSMA-617 has one of the highest binding affinities to the PSMA receptor, which have been published, so far. In preclinical studies, tumor-to-background ratios of up to 1,058 were observed at 24h post infusion. In addition, the internalization of the PSMA-617 into the PCa cells is highly effective: Internalized fraction: 17.67 ± 4.34 % IA/106 LNCaP cells (PSMA-11: 9.47 ± 2.56 % IA/106 LNCaP cells)(Eder, Schafer et al. 2012, Benesova, Schafer et al. 2015). Since 2013, ¹⁷⁷Lu-PSMA-617 has been increasingly used for radioligand therapy of metastatic PCa patients in several centers (Bad Homburg, Bonn, Cologne, Freiburg, Heidelberg, Istanbul, Melbourne, LMU Munich, Münster)(Kratochwil, Giesel et al. 2015).

Diagnostic evaluation with ⁶⁸Ga-PSMA-HBED-CC followed by therapy with ¹⁷⁷Lu-PSMA-617 is thus opening a new theranostic potential of nuclear medicine. Initial studies in patients have demonstrated the utility of ¹⁷⁷Lu-PSMA-617 for the treatment of disseminated prostate cancer(Ahmadzadehfar, Rahbar et al. 2015, Kratochwil, Giesel et al. 2015). Dosimetric evaluation has shown that the critical organs are the parotid glands, and that up to 27 GBq (~700 mCi) of ¹⁷⁷Lu-PSMA-617 can be administered without crossing the 30 Gy critical dose threshold to the parotid glands(Kabasakal, AbuQbeitah et al. 2015).

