2.2. PSMA

In PC, the most well established, prostate-restricted, cell surface antigen yet identified is prostate specific membrane antigen (PSMA) (Horoszewicz, Kawinski et al. 1987, Israeli, Powell et al. 1993, Israeli, Powell et al. 1994, Troyer, Beckett et al. 1995, Wright, Haley et al. 1995). PSMA is a trans- membrane protein with a 707-amino-acid extracellular portion. The PSMA gene (FOLH1) is located on the short arm of

chromosome 11.

Although first thought to be entirely prostate-specific, subsequent studies have demonstrated that PSMA is also expressed by cells of the small intestine, proximal renal tubules and salivary glands(Troyer, Beckett et al. 1995). PSMA is expressed in the apical region of normal prostatic cells, the epithelium surrounding prostatic ducts(DeMarzo, Nelson et al. 2003). Dysplastic changes in the prostate result in the expression of PSMA on the luminal surface of prostatic ducts (Huang, Teh et al. 2003, Wu, Xu et al. 2012). Increasing prostate cancer stage and grade result in higher cell membrane PSMA expression (Silver, Pellicer et al. 1997, Bostwick, Pacelli et al. 1998). The eventual progression to advanced prostate cancer and castrate resistance corresponds to further increases in PSMA expression (Evans, Smith-Jones et al. 2011). PSMA expression in prostate cancer cell membranes is 100- to 1000-fold that in normal cells (Silver, Pellicer et al. 1997, Bostwick, Pacelli et al. 1998). Thus, PSMA represents a promising target for imaging and therapy of prostate cancer.

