3.3. Exclusion Criteria

1. Implantation of investigational medical device ≤ 4 weeks of Treatment Visit 1 (Day 1) or current enrollment in oncologic investigational drug or device study
2. Use of investigational drugs ≤ 4 weeks or < 5 half-lives of Cycle 1, Day 1 or current enrollment in investigational oncology drug or device study
3. Prior systemic beta-emitting bone-seeking radioisotopes
4. Known active brain metastases or leptomeningeal disease
5. History of deep vein thrombosis and/or pulmonary embolus within 1 month of C1D1
6. Other serious illness(es) involving the cardiac, respiratory, CNS, renal, hepatic or hematological organ systems which might preclude completion of this study or interfere with determination of causality of any adverse effects experienced in this study
7. Radiation therapy for treatment of PC ≤ 4 weeks of Day 1 Cycle 1

8. Patients on stable dose of bisphosphonates or denosumab, which have been started no less than 4 weeks prior to treatment start, may continue on this medication, however patients are not allowed to initiate bisphosphonate/Denosumab therapy during the DLT-assessment period of the study.
9. Having partners of childbearing potential and not willing to use a method of birth control deemed acceptable by the principle investigator and chairperson during the study and for 1 month after last study drug administration
10. Currently active other malignancy other than non-melanoma skin cancer. Patients are considered not to have “currently active” malignancy if they have completed any necessary therapy and are considered by their physician to be at less than 30% risk of relapse.
11. Known history of known myelodysplastic syndrome

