6.2.4. Dose levels for ^{177}Lu -PSMA-617

Subject(s) enrollment will be done as 3+3 study design at each dose level. Initially at least 3 subject(s) will be enrolled in Cohort 1 (100 mCi or 3.7 GBq x2 doses 2 weeks apart) with dose escalation (or de-escalation as described above in Section 4 / Table 7).. The enrollment ceiling of the dose escalation portion of the study is up to 46 study participants (six groups, with 3+3 at each dose level). Additional 10 subjects will be enrolled at the MTD dose level to further assess safety and tolerability and to obtain a preliminary assessment of efficacy. Each patient would receive 2 doses of the investigational agent, 2 weeks apart. The total dose received in 2 treatments in phase 1 will be 100 – 600 mCi or 3.7 – 22.2 GBq. The total dose for phase 2 is 600 mCi (22.2 GBq).

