8. DOSING DELAYS/DOSE MODIFICATIONS

There will be no dosing modifications. Unless there are specific reasons not to do so, all patients who are eligible for the trial will receive 5 ± 2 mCi (185 ± 74 MBq) of ^{68}Ga - PSMA-HBED-CC during the Screening Visit and the Efficacy/Scan visit. During the treatment phase, the subject will receive ^{177}Lu -PSMA-617 x 2 doses based on the dose-level/Cohort to which he is assigned. The study chair must clear any dosing delays due to logistical issues (e.g. subject scheduling and/or radionuclide shipping that fall outside of a 2-day window).

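### Section 3.3 sets no limit on earlier PSMA radioligand therapy, so a pretreated man can enter and, on a simple sum, pass the 27 GBq / 30 Gy parotid figure that section 2.4 cites

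*Combined protocol and SAP*

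**What the plan says.** Section 2.2 states that "PSMA is also expressed by cells of the small intestine, proximal renal tubules and salivary glands". Section 2.4 calls the parotids the critical organs for 177Lu-PSMA-617 and, citing a dosimetry study, says that "up to 27 GBq (~700 mCi) of ¹⁷⁷Lu-PSMA-617 can be administered without crossing the 30 Gy critical dose threshold" for those glands.

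Table 7 in section 4.1 sets the two-dose totals, which reach 18.5 GBq in cohort 4 and 22.2 GBq in cohort 5. For the later part of the trial, section 6.2.4 says "The total dose for phase 2 is 600 mCi (22.2 GBq").

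Three items in section 3.3 bear on earlier radionuclide treatment:
- Exclusion 3: "Prior systemic beta-emitting bone-seeking radioisotopes". It has no time limit, but an agent must be both beta-emitting and bone-seeking to fall under it.
- Exclusion 2: "Use of investigational drugs ≤ 4 weeks or < 5 half-lives of Cycle 1, Day 1". This is a washout.
- Exclusion 7: a four-week washout after radiation therapy for prostate cancer.

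Nothing in section 3.2 or the rest of section 3.3 mentions earlier PSMA-targeted radioligand therapy or a lifetime activity. The section on dosing delays says "There will be no dosing modifications". Section 6.4 lets investigators stop a subject at any time on best-interest grounds.

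**The concern.** 177Lu is a beta emitter (Table 4), but the protocol describes PSMA-617 as a PSMA ligand and not as a bone-seeking agent. Exclusion 3 therefore does not reach it. A washout lets the earlier activity decay, but it does not undo the dose already absorbed by the gland. A man treated elsewhere with the study drug can enter, receive the full cohort activity, and end above the critical-organ figure that the protocol itself quotes. No criterion asks anyone to add up his exposure.

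Earlier exposure is plausible, since section 2.4 says the agent has been in growing use at several centers since 2013. The main stake is patient safety, because xerostomia is a listed risk in section 13.1.1. A lesser stake is the secondary objective of relating toxicity to dosimetry (section 1.2), which an unrecorded earlier parotid dose would blur in such a man.

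**Working it through.** **Inputs.**
- Parotid figure: 27 GBq for 30 Gy, also given as about 700 mCi (section 2.4).
- Trial totals: Table 7 and section 6.2.4.
- Earlier activity per dose, multicenter German series (section 2.3.1): "On average, 5.9 GBq was administered per dose (range 2-8 GBq").
- Earlier activity, 28-patient series (section 2.3.1): "Mean administered activity at first therapy was 5.92 ± 0.44 GBq", with a mean of 5.86 GBq at the second therapy.

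**The plan's own figure.** 600 mCi × 0.037 GBq/mCi = 22.2 GBq = 2 × 11.1 GBq. It reproduces.

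**Imprecision in the benchmark.** 27 / 0.037 = 730 mCi, while 700 × 0.037 = 25.9 GBq. Section 2.4 therefore supports either 27 or 25.9 GBq as the 30 Gy point.

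**Implied dose per activity.** 30 / 27 = 1.11 Gy/GBq, or 30 / 25.9 = 1.16 Gy/GBq.

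**Men without earlier treatment, and room left (27 − total; 25.9 − total).**

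| Cohort | Total (GBq) | Gy at 1.11 | Room to 27 | Room to 25.9 |
|---|---|---|---|---|
| 1 | 7.4 | 8.2 | 19.6 | 18.5 |
| 2 | 11.1 | 12.3 | 15.9 | 14.8 |
| 3 | 14.8 | 16.4 | 12.2 | 11.1 |
| 4 | 18.5 | 20.6 | 8.5 | 7.4 |
| 5 / phase II | 22.2 | 24.7 | 4.8 | 3.7 |

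Every level is below 30 Gy without earlier exposure. At 22.2 GBq the 25.9 GBq basis gives 22.2 × 30 / 25.9 = 25.7 Gy.

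**Adding earlier activity.** Lifetime total = earlier + trial; Gy = total × 30 / 27.

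| Earlier 177Lu-PSMA-617 (GBq) | Plus 18.5 | Plus 22.2 |
|---|---|---|
| 2 (low end, one dose) | 20.5 GBq, 22.8 Gy | 24.2 GBq, 26.9 Gy |
| 5.9 (average, one dose) | 24.4 GBq, 27.1 Gy | 28.1 GBq, 31.2 Gy |
| 8 (high end, one dose) | 26.5 GBq, 29.4 Gy | 30.2 GBq, 33.6 Gy |
| 5.92 + 5.86 = 11.78 (two doses) | 30.3 GBq, 33.6 Gy | 34.0 GBq, 37.8 Gy |

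One average earlier dose passes the figure at the phase II dose (32.5 Gy on the 25.9 GBq basis); one 2 GBq dose does not. Two doses pass it in cohort 4 too. The 11.78 GBq is a sum of two means and not any one patient's total. In cohort 3 the same two doses give 14.8 + 11.78 = 26.6 GBq, which is below 27 but above 25.9.

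**Sensitivity to recovery.** The documents give no recovery figure, so this is an assumption. The discount on earlier activity that brings the total back to 27 GBq is 1 − room / earlier:
- at 22.2 GBq: 1 − 4.8/5.9 = 19%; 1 − 4.8/8 = 40%; 1 − 4.8/11.78 = 59%
- at 18.5 GBq: 1 − 8.5/11.78 = 28%

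**Position before the second fraction, phase II dose.** 11.1 + 5.9 = 17.0 GBq; 11.1 + 11.78 = 22.9 GBq. Any earlier activity up to 27 − 11.1 = 15.9 GBq is still at or under the figure at that time.

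**The case against.** The strongest reply is that the exposed group may not exist. Section 2.5 places this treatment mainly in Europe and Australia, and the title page lists only US sites. The benchmark is also soft. It is one background sentence, no rule in the protocol refers to it, and the documents do not say that 30 Gy applies across separated courses. A 19% discount removes the single-dose example. All of this stands, and it is why the point is minor.

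A reader might infer that eligibility is the only place to act in advance, because dosing cannot be modified. The documents do not support that. The statement on modifications does not forbid withholding the second fraction, section 6.4 permits stopping a subject, and the Day 8 imaging falls between the fractions. In the phase II examples above, the man is still below 27 GBq at that stage. What is missing is any rule that makes the investigator consider earlier activity.

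A reader might also infer that the cited clinical experience lies well below 22.2 GBq. That would compare single doses with a two-dose total. Table 6 includes 43 men given 6 GBq for one to four doses, which is up to 24 GBq. Section 2.5 reports no attributable grade 4 toxicity with repeat dosing, and section 2.6 describes the reported toxicities as mild and transient. This is real reassurance at around the trial's own total. It does not settle parotid tolerance above 27 GBq, because Table 6 counts only hematologic events and the reported follow-up is at most six months.

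Finally, a grade 3 or worse related non-hematologic event is a DLT and ends treatment. That rule acts only after harm has appeared.

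**Conclusion.** The gap is real and the arithmetic holds: the written criteria admit a man whose lifetime 177Lu-PSMA-617 activity would pass the parotid figure in section 2.4. The room is 4.8 GBq at the phase II dose (3.7 on the 700 mCi reading) and 8.5 GBq in cohort 4 (7.4). The excess is 1.1 GBq, or 1.2 Gy, after one average earlier dose at 22.2 GBq, and 7.0 GBq after two.

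This rests on linear dose per GBq, no recovery between courses, and the cited figure being a fair guide to cumulative exposure. It does not apply to earlier 177Lu-J591, a full-length antibody that section 2.5 expects to distribute differently.

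A reader might take this to mean that the trial breaches a dose limit or overdoses its population. It does neither: 27 GBq is not a protocol cap, and men without earlier PSMA radioligand therapy stay below it throughout. The conclusions of the trial are not at risk. This is a low-severity, inexpensive safety improvement.

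**What to change.** Add one exclusion to section 3.3, applying to all dose levels:

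> *Prior 177Lu-PSMA-617 if documented prior cumulative activity plus the planned two-dose activity exceeds 27 GBq, or if prior activity cannot be documented; prior therapeutic (not diagnostic) use of any other radiolabeled small-molecule PSMA ligand.*

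If the sponsor regards 700 mCi as the intended figure, 25.9 GBq should replace 27. The second part is needed because section 2.3 describes 131I- and 225Ac-labeled PSMA ligands as therapies and the documents reviewed give no parotid figure that would allow a sum for them. It is a precaution and not a calculated limit. The word therapeutic keeps the screening 68Ga scan permissible. One rule for all levels also treats phase I patients at the MTD consistently, since section 12.2 counts them in phase II.

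Record the sum on the signed eligibility checklist already required by section 5.3. Section 6.1.1 already collects earlier systemic drugs, doses and dates, so no test, visit or extra patient is needed. The cost is that a few pretreated men, possibly none, cannot enter.
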